Leber Hereditary Optical Neuropathy (LHON) is an inherited mitochondrial disease of partial penetrance affecting both genders with predominance in males (~80%). The pathophysiology of LHON mainly affects the retinal ganglion cells (RGCs). The ND4 G11778A mutation is responsible for the majority of cases (~70%). Vision loss classically occurs in a bilateral sequential fashion, the second eye becoming involved after the first one with a median delay of 2 months. GenSight Biologics' strategy to specifically treat LHON is based on a gene therapy approach by the development of GS010. The scientific basis behind this Investigational Medicinal Product consists of rescuing mitochondrial function by reaching the nucleus of the target cell, forming intranuclear episomes that can be read and produce specific mRNA inducing ND4 protein synthesis and targeting of the ND4 protein to the mitochondria. This is expected to significantly improve the respiratory chain function. Preclinical studies performed in rats strongly suggest that GS010 displays a potential to restore wild-type ND4 expression.

Study Treatment: GS010 is a recombinant adeno-associated viral vector serotype 2 (rAAV2/2) containing the wild-type ND4 gene (rAAV2/2-ND4). In this study, subjects will receive a single dose of GS010 via intravitreal (IVT) injection containing 9E10 vg in 90µL balanced salt solution (BSS) plus 0.001% Pluronic F68[®].

Target Population:

The study population will be subjects with LHON due to the G11778A *ND4* mutation who have been affected by vision decline for 180 days or less.

Number of Subjects:

It is planned that approximately 40 subjects will be screened in order to randomize 36 into the study at 7 sites (one each in France, Germany, Italy, and the United Kingdom and 3 in the United States).

Objectives: Primary Objective:

To evaluate the efficacy of GS010 compared with sham at Week 48 in the change from baseline of the Log of the Minimal Angle of Resolution (LogMAR) in subjects affected for 6 months or less by LHON.

Secondary Objectives:

- To evaluate the efficacy of GS010 compared with sham over the follow-up period and at Week 96 in the change from baseline of the LogMAR.
- To verify whether the efficacy at Week 48 and at Week 96 of GS010 compared with sham and measured by the change from baseline in the LogMAR is dependent upon the treatment of the better- or worse-seeing-eye.

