4 STUDY PLAN

4.1 Study Design

GS-LHON-CLIN-03A is a Phase III double-masked, sham-controlled, multicenter, multicountry, study. Recruitment is competitive.

Both eyes will receive standard antiseptic preparation, administration of topical local ocular anesthetic agents and will undergo pupillary dilation. Administration of an IOP lowering agent will precede treatment. GS010 will be administered once during the study via a single IVT injection. Sham IVT injection will be performed whereby pressure will be applied to the eye at the site of a typical procedure using the blunt end of a syringe without a needle.

The right eye of each subject will be randomly allocated to receive either GS010 or sham treatment in a 1:1 allocation ratio. The fellow (left) eye will receive the treatment not allocated to the right eye. Therefore, each subject will receive GS010 in one eye and sham treatment in the fellow eye.

An algorithm with a testing hierarchy will be employed to determine the better- and worse-seeing eye of each subject prior to randomization. The randomization will be based on the right and left eye, because if the right eye is treated the left eye will receive sham and vice versa the treatment groups will be automatically balanced. However, the better- or worse-seeing eye at entry can be a confounding factor, and it cannot be discarded that the treatment effect will be the same in the better and worse seeing-eye. Secondarily, in order to verify this hypothesis, an adaptive randomization technique called Efron's minimization method will be used to minimize the imbalance of treatment groups between the better-seeing eyes treated and worse-seeing eyes treated.

Masking will be accomplished with sham injection of the fellow eye. Thus, treatment allocation will be double-masked for both the subject and the investigation (follow-up) team. The pharmacy team, as well as the physician and medical team performing the GS010 administration and sham injection will be unmasked to treatment allocation. This treating, unmasked medical team will also perform the first follow-up visit (Visit 4), as well as focused follow up of ocular adverse events commencing at Visits 3 and 4 until

resolution of the AE or the determination that no further clinical evolution is expected. Centralized analysis of ETDRS, automated visual fields, SD-OCT, color vision and contrast sensitivity will be performed.

Trial visits:

The trial is divided into the following visits:

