5.2 Selection for the Study

5.2.1 Selection Criteria

Subjects must meet all the following criteria at the Screening Visit (Visit 1) in order to be included into the study.

- 1. Age 15 years or older.
- 2. Onset of vision loss based on medically documented history or subject testimony, in at least one eye for ≤ 180 days in duration and if both eyes are affected the duration of vision loss in both eyes must be ≤ 180 days in duration.
- 3. Each eye of the subject maintaining visual ability to allow at least for counting of the examiner's fingers at any distance.
- 4. Female subjects (if of childbearing potential) must agree to use effective methods of birth control up to 6 months after IVT injection and male subjects must agree to use condoms for up to 6 months after IVT injection.
- 5. Ability to obtain adequate pupillary dilation to permit thorough ocular examination and testing.
- 6. Signed written informed consent.

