A meta-analysis combining study GS-LHON-CLIN-03A (RESCUE) and study GS-LHON-CLIN-03B (REVERSE) is planned to verify whether the treatment effect at Week 48 as well as at Week 96 is dependent upon the time from onset of disease. If the treatment effect does not depend upon the eye status, a model using the change from baseline as the response, the subject as a random factor, the treatment as a fixed factor, the time from the onset of disease as a covariate and the interaction between the treatment and the time from the onset will be fitted. If the treatment effect is not the same in the better-and worse-seeing eye, a model will be fitted for the better-seeing eye and another model will be fitted for the worse-seeing eye. The subject factor will not be included in the model, but the LogMAR at baseline, the treatment, and the time from onset of disease will be included.

The generalizability of the treatment effect across countries will be addressed in the metaanalysis because the number of subjects per country could be sufficient to detect major heterogeneity.

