12.4.2 Secondary Analysis

The treatment estimate at Week 96 will be based on the same statistical approach as the primary endpoint analysis. Another analysis will compare time course of the response up to Week 96 using the mixed model procedure. The responder analyses at both Week 48 and Week 96 will be based on a McNemar test for paired samples. To verify whether the treatment effect is dependent upon the better-seeing eye or the worse-seeing eye at study entry, a test of homogeneity of subgroups (better-seeing or worse-seeing eye treated) effects in stratified paired binary data (Zhao 2014) will be performed.

Like the primary endpoint, a meta-analysis will be performed combining both studies (GS-LHON-CLIN-03A (RESCUE) and study GS-LHON-CLIN-03B (REVERSE). A conditional logistic model will be used to assess the effect of better- and worse-seeing eye at study entry and the effect of time from onset of disease and the effect of treatment.

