## Vision Loss Duration at Screening

Vision loss duration in days will be based on the difference between the date of onset of vision loss per eye and Screening date.

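### The pooled responder model lists time from onset only as a main effect, so it cannot test whether the GS010 effect depends on time from onset

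*Protocol*

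**What the plan says.** Protocol 12.4.2 presents the pooled responder analysis as the counterpart of the pooled primary-endpoint analysis. The model is given in one sentence: "conditional logistic model will be used to assess the effect of better- and worse-seeing eye at study entry and the effect of time", where time means time from onset. The terms named after eye status are "the effect of time from onset of disease and the effect of treatment". No interaction is listed, the conditioning stratum is not named, and time from onset is not said to be per subject or per eye.

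Protocol 12.4.1 gives the purpose of pooling for LogMAR: to see whether the treatment effect at Weeks 48 and 96 depends on time from onset. If the effect does not differ by eye status, the model there has a random subject factor, treatment, and "the time from the onset of disease as a covariate and the interaction between the treatment and the time from the onset will be fitted".

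Three other places bear on the point:

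- Protocol 4.1: "each subject will receive GS010 in one eye and sham treatment in the fellow eye".
- SAP 5.6, Vision Loss Duration at Screening: duration rests on "the difference between the date of onset of vision loss per eye and Screening date".
- The protocol's study summary describes "the second eye becoming involved after the first one with a median delay of 2 months", and selection criterion 2 (Protocol 5.2.1) adds that "if both eyes are affected the duration of vision loss in both eyes must be" within the 180-day limit. That criterion asks for vision loss in at least one eye, so a second eye may be unaffected at entry.

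**The concern.** Conditional logistic regression on matched pairs discards everything that the two members of a pair share. Time from onset varies largely between subjects and, by design, between the two studies being pooled. Using it as a main effect in such a model removes the variation that pooling was meant to supply. A main effect is also not effect modification. Without a treatment-by-time term, the model assumes a constant treatment odds ratio over time from onset, when that constancy is the question.

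If the sentence is programmed as written, there are two possible outcomes. The software may drop the time term, and a reader may take its absence as evidence of no effect. Or it may return a coefficient based on the gap between eyes, which a reader may take as the answer on early versus late treatment.

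**Working it through.** The plan gives no figure for this analysis, so the check is on which coefficients the model can identify.

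**Inputs.** One GS010 eye and one sham eye per subject (Protocol 4.1). Terms: treatment T, eye status E, time from onset t (Protocol 12.4.2). Planned pairs: 36 + 36 = 72 (SAP 3.3). Assumption: the stratum is the subject.

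**Likelihood.** Only pairs in which exactly one eye responds contribute. For such a pair,

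P(the GS010 eye is the responder) = 1 / (1 + exp(−β′d)), with d = x(GS010 eye) − x(sham eye).

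**Within-pair differences** (T = 1 for GS010 and 0 for sham; E = 1 for better and 0 for worse):

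| Term | d |
|---|---|
| T | 1 − 0 = 1 in every pair |
| E | +1 if the better eye gets GS010, −1 if the worse eye does |
| t, one value per subject | t − t = 0 |
| t, per eye | t_GS − t_sham |
| T × t, one value per subject | 1·t − 0·t = t |
| T × t, per eye | 1·t_GS − 0·t_sham = t_GS |
| T × E | 1 or 0, that is (d_T + d_E)/2 |

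**Reading 1: one time per subject.** The linear predictor is β_T ± β_E + 0·β_t. The time column is all zeros, so {T, E, t} has rank 2 of 3. The main effect of time has no estimate.

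**Reading 2: time per eye.** The linear predictor is β_T ± β_E + β_t(t_GS − t_sham). {T, E, t} has rank 3 of 3, so β_t is estimable. Now add any constant c to both eyes' times: (t_GS + c) − (t_sham + c) = t_GS − t_sham. The likelihood does not change. How early or late a subject is overall, and which of the two studies the subject belongs to, therefore contribute nothing to β_t. The information comes only from the gap between the eyes, for which the protocol gives a median delay of 2 months. For two eyes with equal onset times, the GS010 log odds ratio is β_T ± β_E whatever that common time is.

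**With the interaction added.**

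- One time per subject, {T, E, T × t}: β_T ± β_E + β_Tt·t, rank 3 of 3.
- Time per eye, {T, E, t, T × t}: rank 4 of 4, whether the interaction uses a subject-level time or the eye's own time.

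The log odds ratio now depends on t, so the question can be tested.

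**Why a per-eye main effect must stay.** With both terms, the time part is β_t(t_GS − t_sham) + β_Tt·t_GS = (β_t + β_Tt)·t_GS − β_t·t_sham. If the main effect is dropped while β_t is not zero, the interaction coefficient absorbs part of it.

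**Precision (illustration only).** Assumptions not in the documents: exponential inter-eye delay with median 2 months, REVERSE onset 181 to 365 days, log-odds coefficients of −0.15 per month for per-eye time and −0.20 per month for treatment by time, and chosen values for the rest. With 720 simulated pairs the median estimates were −0.152 and −0.198, so both terms are recovered. With 72 pairs, about 28 to 29 were discordant and the median standard errors were about 0.17 and 0.15. The assumed effects are then about 0.15/0.17 = 0.9 and 0.20/0.15 = 1.3 standard errors. Some simulated fits did not converge or showed separation, so these figures are rough.

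**The case against.** The best defence has four parts.

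**Per-eye time.** The SAP derives vision-loss duration from each eye's onset date, and SAP 9.3 summarises it for all GS010 versus all sham eyes, which is informative in a fellow-eye design only if duration differs between eyes. A per-eye coefficient is estimable. This stands. A reader might infer that the model can give no time-from-onset effect at all; the documents do not support that, because the loss is complete only for a main effect of a time shared by both eyes.

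**Carry-over from the LogMAR analysis.** Protocol 12.4.2 likens the pooled responder analysis to that of the primary endpoint, so the interaction may have been meant. Protocol 12.1 leaves detail to the SAP, and parts of the SAP are redacted. Nothing can be concluded from the lack of a pooled responder model in the visible SAP text. But Protocol 12.4.2 does name its terms, and the interaction is not among them.

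**Eye status.** T × E is an exact combination of T and E within pairs ({T, E, T × E} has rank 2 of 3), so a reader might infer that the plan cannot examine responder effects by eye status. That does not follow. T × E is not a listed term, and the same section gives the trial's eye-status question a separate homogeneity test for stratified paired binary data. Nor do the documents show that per-eye time would largely duplicate eye status: Protocol 8.6 sets status by acuity, then OCT, then contrast sensitivity, not by order of onset.

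**Weight.** This is a supportive pooled analysis of a secondary endpoint, and SAP 9.5.3 spends all of alpha on the primary endpoint. That stands and limits the consequence.

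**Conclusion.** The point holds in a limited form. As listed, the pooled responder model does not test whether the GS010 effect on response depends on time from onset. With one time per subject, the listed time effect is not estimable. With a time per eye it is estimable, but it reflects only differences between a subject's two eyes and is still not effect modification.

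The conclusion assumes that the subject is the stratum, which the paired design implies but the protocol does not state. The rank results for the fuller models need only that onset times vary between subjects and, for per-eye time, differ within some pairs. They do not depend on the simulation.

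The primary analysis and the pooled LogMAR model are unaffected. The correction should be made because the stated model cannot answer the question for which the studies are pooled, and the remedy is already written one section earlier.

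**What to change.** In Protocol 12.4.2, and in the SAP or pooled-analysis plan that implements it:

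1. State that the stratum is the subject.
2. Add treatment by time from onset to the conditional model, keeping treatment and eye status.
3. Say whether time from onset is per eye or per subject, and which version enters the interaction. If per eye, keep its main effect and state how an eye not yet affected is coded. If per subject, drop its main effect from the conditional model.
4. If a between-subject effect of time is wanted, add a supportive eye-level logistic GEE or a random-intercept logistic model, with subject as the cluster. The same model would serve if treatment by eye status is wanted in the pooled data.

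The cost is a few lines of text, one added term and, if chosen, one supportive model. No new data are needed. The drawback is an imprecise interaction estimate, to be reported with its confidence interval and not read as absence of effect when non-significant. Protocol Appendix V bars SAP amendments once the randomization code is broken and treats later additions as ad hoc, so the change keeps its prespecified standing only if made before then.

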12.4.3 Analysis of Vision-Related Secondary Endpoints

SD-OCT will be presented by summary statistics for continuous data. Visual field data generated from HVF analyzer II, Goldmann applanation tonometry, color vision, and contrast sensitivity data will be summarized between the two treatments by using descriptive statistics.

12.4.5 Analysis of Safety

Incidence and severity of all treatment and non-treatment emergent local and systemic AEs and SAEs will be presented by system organ class and preferred term. Summary descriptive

[figure not shown]
statistics will be presented for all continuous variables. The visual testing at Visit 4 will be conducted for safety purposes and will not be analyzed as efficacy data (see Section 7.6.3).

All AEs will be coded using the most up-to-date version of the Medical Dictionary for Regulatory Activities (MedDRA). Only AEs occurring after administration of IMP will be included in the safety analysis.

The incidence of AEs (number and percent of subjects reporting the AE at least once during the study) will be summarized by body system and preferred term for all AEs, by the Investigator's attribution of relationship to study drug and by severity. The details will be included in the statistical analysis plan.

12.4.5.1 Laboratory Data

At each visit where clinical laboratory assessments are conducted, summary statistics for the absolute laboratory value and the changes from baseline will be presented. Statistical testing will be performed at the Visit 12/end of study visit. Shift tables will be presented to compare the shifts between the baseline and post-baseline visits. Clinically significant abnormal lab values for different parameters will be summarized.

Concomitant medication verbatim terms on CRFs will be mapped to Anatomical Therapeutic Chemical Level 4 categories and Drug Reference Names using the World Health Organization (WHO) dictionary (Version December 1, 2006). Incidence (number and percent of subjects reporting the medication at least once during the study) will be summarized for all concomitant medications.

12.4.6 Demographic and Baseline Characteristics

Demographic and baseline characteristics (gender, age, weight, height) will be summarized using descriptive statistics. Qualitative variables (gender) will be summarized using frequencies while quantitative variables (age, weight) will be summarized using mean, SD, median, Q1, Q3, minimum, and maximum.

12.5 Interim Analysis

No interim efficacy analyses are planned.

12.6 Timing of Primary Analysis

Primary endpoint analysis will be performed as soon as the last subject completes the Week 48 assessment and data are cleaned. At that point, all subjects will be recruited and followed for at least 48 weeks except in case of premature withdrawal. Many subjects will have reached Week 96 but not all of them. The study will be formally unmasked for the efficacy analysis at Week 48 to allow an early registration if results meet the expectations. The study will still continue up to scheduled end (Week 96). Although the study will have been unmasked for the study statistician, every effort (see Appendix V in Section 20.5) will be invested to maintain the masking of subjects and personnel in charge of the conduct of the study including study managers, data managers, CRAs, investigators (except international coordinating investigators per Appendix V in Section 20.5). After the completion of the study, only the analyses related to the Week 96 endpoints will be performed (see Appendix V in Section 20.5).

12.7 Handling of Missing Data

In case of missing data at Week 48, the following rules will be applied in the first imputation method:

Rule 1: If the LogMAR is available at the previous and the following visits then the imputed value at Week 48 will be a linear interpolation of LogMAR.

Rule 2: If there is no following visit due to drop out then the relative change (RC_i) from visit V_i to visit V_{i+1} will be calculated at each visit from the baseline to the visit preceding Week 48 in the group treated with a sham. The last available visit (V_i) with data (X_i) will be used as the starting time point. The imputed score at V_{i+1} for each eye will be equal to $X_{i+1} = X_i * RC_i$. The imputed score at the next missing visit V_{i+2} will be equal to $X_{i+2} = X_{i+1}*RC_{i+1}$, and so on up to Week 48 visit. The RC_i will be the same for the treated and sham eyes.

With the first method of imputation the between eye difference at Week 48 will be proportional to the between eye difference at the time of withdrawal because the same RC_i coefficients are used for both eyes.

The second imputation method leading to an additional sensitivity analysis will apply the same Rule 1 but Rule 2 will be based on the evolution of the difference between treated and sham eye. RC_i is then the relative change from visit i to visit i+1 of the difference between treated and sham eye in all subjects attending visit i and i + 1. The sensitivity analysis will be a one sample t-test performed on the difference between treated and sham eyes at Week 48. This method assumes that the evolution of drop-out is similar in terms of between eye differences to that of subjects who were followed-up.

The third imputation method will apply the same Rule 1 but for Rule 2 the last available data will be carried forward for the sham eye and the worst available value (either sham or treated eye) will be carried forward for the treated eye. This should be the most conservative imputation method.

13 ETHICS AND RESPONSIBILITIES

13.1 Good Clinical Practice

The current study will comply with the International Conference on Harmonisation (ICH), Good Clinical Practice (GCP), and applicable regulatory requirements.

The Investigator is responsible for ensuring that the clinical study is performed in accordance with the protocol, current ICH GCP guidelines, and applicable regulatory and country-specific requirements. GCP is an international ethical and scientific quality standard for designing, conducting, recording, and reporting studies that involve the participation of human subjects. Compliance with this standard provides the public assurance that the rights, safety, and well-being of study subjects are protected, consistent with the principles that originated in the Declaration of Helsinki and that the clinical study data are credible.

